8.3.7 Adverse Events of Special Interest (Not Applicable)

No AEs of special interest are defined for this study.

8.3.8 Medical Device Deficiencies (Not Applicable)

The medical device to be used in this study is a vibrating mesh nebulizer that is FDA-approved and CE marked and is to be used per the manufacturer's recommendations. Therefore, data on device deficiencies will not be collected in this study.

8.4 Tokenization (Optional)

Tokenization is the process of converting a piece of data into a random string of characters known as a token. Tokenization protects sensitive data by substituting non-sensitive data. The

token serves merely as a reference to the original data, but cannot be utilized to determine those values. The advantage of tokens is that there is no mathematical relationship to the real data that they represent. The real data values cannot be obtained through reversal, and hence, a breach renders the information invaluable. Tokens are being increasingly used to secure varying types of sensitive information. In particular, personal identifiable information such as healthcare information, email addresses and account numbers are such examples. From a security perspective, tokenization significantly reduces risk based on the fact that sensitive data cannot be breached if it is not there in the first place.

Tokenization applies only to US participants who agree and sign the optional ICF. The piece of personal data needed to generate the token will be collected to create a unique, de-identified token. This token would be instrumental to enrich and aggregate other study participants' data coming from different sources for the purpose of future research. The benefit of linking data in general, is that the data set that is created can be used to answer a variety of healthcare- and therapy-related questions that could not otherwise be answered through conventional means.

8.5 Treatment of Overdose (Not Applicable)

There is no risk of overdose.

8.6 Pharmacokinetics (Not Applicable)

Pharmacokinetic parameters are not evaluated in this study.

8.7 Pharmacodynamics (Not Applicable)

Pharmacodynamic parameters are not evaluated in this study.

8.8 Genetics (Not Applicable)

Pharmacogenomics are not evaluated in this study.

8.9 Biomarkers (Not Applicable)

Biomarkers are not evaluated in this study.

8.10 Medical Resource Utilization and Health Economics (Not Applicable)

Health Economics/Medical Resource Utilization and Health Economics parameters are not evaluated in this study.

9 Statistical Considerations

9.1 Statistical Hypothesis

RESP301 reduces the rate of progression to level 5 and above in the modified WHO ordinal scale in COVID-19 (see Section 8.1.1).

This represents a composite endpoint of (i) death (level 7), (ii) hospitalized, on invasive mechanical ventilation or ECMO (level 6), or (iii) hospitalized, on non-invasive ventilation or high-flow oxygen devices (level 5).

9.2 Sample Size Determination

A total of 300 hospitalized participants with confirmed COVID-19 will be randomized 2:1 to receive RESP301+SOC (200 participants) or SOC alone (100 participants).

The comparison between the treatment arms for the primary endpoint will have approximately 80% power and alpha level 0.025 (one-sided) to demonstrate significant reductions (15% versus 30%) of the primary endpoint between RESP001+SOC and the Control arm (SOC), a 50% relative reduction for the proportion of participants who progress to level >4 (see definition of the primary endpoint).

Two interim analyses are planned (see Section 9.5 for details):

1. The first IDMC interim analysis will take place after the first 60 participants have completed Day 10 of the study to evaluate whether the study can be stopped for futility based on change from baseline in room air SpO₂. For a final decision to stop the study for futility the results on other endpoints will be considered as well.
2. The second interim analysis will take place after 150 participants have completed Day 14 post-randomization based on event rate for the primary endpoint. The purpose of the second interim analysis will be futility as well as a potential sample size re-estimation in case the actual results differ from the original assumptions.

In addition to the review of efficacy data, safety will be assessed at each of the interim analysis by the IDMC. Further details are provided in Appendix 5.

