9.5 Interim Analyses

Two interim analyses will be performed.

1. The first analysis will be conducted when about 60 participants (40 participants in the RESP301+SOC arm and 20 participants in the SOC arm) have completed the Day 10 assessment. The purpose of this analysis is to evaluate efficacy of RESP301 with the application of a futility criterion based on the results on SpO₂ change from baseline on Day 10. The following futility criterion will be used for this first interim analysis:

If the difference in the percentage of participants with at least a 2% improvement in SpO₂ between both treatment arms is less than 5%, benefit of RESP301 treatment is not expected. For a final decision to stop the study for futility the results on other endpoints will be considered as well.

As no other modification of the study at the time of the first interim analysis is considered, no adjustment of the alpha level is required.

2. The second interim analysis will be conducted after 150 participants (100 participants in the RESP301+SOC arm and 50 participants in the SOC arm) have completed the Day 14 assessment. The purpose of this analysis is the assessment of futility or a sample size re-estimation in case the actual results differ from the original assumptions for the power calculations of the study, related to the percentage of participants meeting the primary endpoint in the control arm and/or the relative treatment benefit achieved in the RESP301+SOC arm compared to the SOC arm.

To account for the multiple testing due to the second interim analysis an adjustment for the type I error alpha will be applied using the Haybittle-Peto approach which would spend one sided alpha=0.0005 at the second interim analysis and leave one-sided nominal alpha of 0.0249 for the final analysis. The futility criterion for the second interim analysis will be based on the conditional power (CP) for the final results based on the assumption that the remainder of the study will follow the same trend as observed in the interim analysis. If CP at the time of the second interim analysis is less than 20% consideration

will be given to stop the study for futility. At the same time sample size re-estimation will be performed to achieve 80% power at the end of the study. The methodology for the adjustment and the procedure to maintain the type I error level will be described in greater detail in the SAP.

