3. Non-binding DMC guidance for stopping the study for futility at the first interim analysis is stated as:

If the difference in the percentage of participants with at least a 2% improvement in SpO₂ between both treatment arms is less than 5%, a benefit of RESP301 treatment is not expected. For a final decision to stop the study for futility the results on other endpoints will be considered as well.

As the main futility stopping criterion is based on improvement in SpO₂ (and not on the primary efficacy endpoint), this first interim analysis will be “ignored” in these statistical considerations for an adaptive group-sequential design. We may revisit the first interim analysis at a later point in time when more information is available.

4. Non-binding DMC guidance for stopping the study for futility at the second interim analysis stated as:

The futility criterion for the second interim analysis will be based on the conditional power (CP) for the final results based on the assumption that the remainder of the study will follow the same trend as observed in the interim analysis. If CP at the time of the second interim analysis is less than 20% consideration will be given to stop the study for futility.

5. Current DMC guidance for stopping the study for superior efficacy at the second interim analysis is stated as:

To account for the multiple testing due to the second interim analysis an adjustment for the type-I-error probability will be applied using the Haybittle-Peto approach with one sided alpha=0.0005 at the second interim analysis and leave one-sided nominal alpha of 0.0249 for the final analysis.

6. For initial sample size calculation, the following additional assumptions / features from the protocol have been used

- progression probability up to Day 14 for Standard of Care (SOC): 30%

- progression probability up to Day 14 for RESP301+SOC: 15%
- desired power assuming the alternative hypothesis stated above: 80%
- 2:1 randomization

7. Method for adaptation of the sample size based on the second interim analysis data is stated as

A sample size re-estimation will be performed to achieve 80% conditional power at the end of the study. The methodology for the adjustment and the procedure to maintain the type-I-error level will be described in greater detail in an appendix to the protocol. The maximum increase of the sample size will be limited to a total number of 600 randomized subjects.

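### The approximately 80% power in 9.2 was computed with the first-interim SpO2 futility look left out, and that look's criterion is very noisy at 40 versus 20 participants

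*Protocol*

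**What the plan says.** References are to the Amendment 1 text, the latest in which the statistical sections are shown. The Amendment 2 summary of changes lists nothing for 9.2, 9.5 or Appendix 5.

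- **Section 9.2** states: "The comparison between the treatment arms for the primary endpoint will have approximately 80% power and alpha level 0.025 (one-sided"), for "significant reductions (15% versus 30%) of the primary endpoint". Participants "will be randomized 2:1 to receive RESP301+SOC (200 participants) or SOC alone (100 participants"). It then lists two interim analyses, the first to judge futility from room-air SpO2, and adds that other endpoints will be considered before a final decision to stop. It refers to Appendix 5 for details.
- **Section 9.5, item 1** places the first look at "about 60 participants (40 participants in the RESP301+SOC arm and 20 participants in the SOC arm") with Day 10 data. If the difference in the percentage with at least a 2% SpO2 improvement "between both treatment arms is less than 5%, benefit of RESP301 treatment is not expected". The sentence about other endpoints is repeated.
- **Section 9.5, item 2** spends one-sided 0.0005 at the second look, would "leave one-sided nominal alpha of 0.0249 for the final analysis", and sets second-look futility at conditional power (CP) below 20%.
- **Appendix 5 (10.5.1, item 3)** labels the first-look rule non-binding guidance and sets that look aside in the design calculations because it is not based on the primary endpoint. It adds: "We may revisit the first interim analysis at a later point in time when more information is available".
- **Appendix 5 (10.5.2)** enters NA for the first look's futility stopping probabilities. For the second look, with futility at CP below 4%, it gives 70% under no effect, 6% under 30% versus 15%, and 10% for early superiority.

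**The concern.** The stated power describes a trial with one interim look and a final analysis. The trial to be run has an earlier look that can end it for futility. A futility look cannot raise power. It lowers power whenever it stops a trial that would have succeeded.

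The size of that loss depends on how often chance alone meets the criterion. With 20 controls, one participant is 5 percentage points, which is the whole threshold. The protocol gives no expected SpO2 responder rates and does not say how a 2% SpO2 improvement relates to progression. A committee told that benefit is not expected would therefore not know how often that signal appears when the drug works. At stake is an early stop of an effective treatment at 60 participants, and a power figure that omits this risk.

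**Working it through.** **Inputs from the protocol.** Progression 30% (SOC) and 15% (RESP301+SOC); 100 and 200 participants; first look at 20 and 40; second look at 50 and 100; one-sided nominal levels 0.0005 and 0.0249; second-look futility at CP < 4% (Appendix 5) or < 20% (9.5).

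**Assumed, because not stated.** Control SpO2 responder rate 20-60%; true responder advantage 0, 10, 15 or 20 points; latent correlation between SpO2 response and non-progression 0 to 0.8.

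**1. Reproduce the stated power without the first look.**
Unpooled SE = √(0.30×0.70/100 + 0.15×0.85/200) = √0.0027375 = 0.0523.
Power = Φ(0.15/0.0523 − 1.96) = Φ(0.907) = 81.8%.
Continuity-corrected gives 81.3%, Fisher exact 81.4% and pooled z 84.9%.
Simulating the second look (CP < 4%, p < 0.0005) and the final analysis gives 81.5% (unpooled) or 83.3% (pooled). With sample size re-estimation it is 83-85%. The same simulation gives second-look futility of about 6% under 30% versus 15% and 69-71% under no effect, against 6% and 70% in 10.5.2. The published characteristics are therefore those of the design without the first look.

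**2. Noise in the first-look criterion.**
SE = √[pT(1−pT)/40 + pC(1−pC)/20].
At pC = 0.40, pT = 0.55: √(0.0061875 + 0.012) = 0.135.
Over control rates of 10-80% with a 15-point advantage, the SE is about 10 to 13.5 points, two to nearly three times the 5-point threshold.

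**3. Probability that the criterion is met.** Sum the product of the two binomial probabilities over all outcomes with x/40 − y/20 < 0.05.

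**4. Power if every flag stopped the trial.** With zero correlation the flag is independent of progression, so power = 0.833 × (1 − flag probability). At a control rate of 40%:
- no SpO2 effect: 0.833 × (1 − 0.607) = 33%
- 10 points: 0.833 × (1 − 0.320) = 57%
- 15 points: 0.833 × (1 − 0.202) = 66%
- 20 points: 0.833 × (1 − 0.114) = 74%

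Positive correlation adds one to two points; the unpooled test takes off one to two.

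| True SpO2 advantage | Criterion met (control 20-60%) | Power, flags not acted on | Power, every flag stops |
|---|---|---|---|
| 0 points | 61-63% | 81-84% | about 33% |
| 10 points | 29-32% | 81-84% | about 57% |
| 15 points | 17-20% | 81-84% | about 67% |
| 20 points | 9-11% | 81-84% | about 74% |

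**5. Power if a stop also needs an unfavourable trend.** Suppose the trial stops only if the criterion is met and observed progression on RESP301 is no better than on SOC. This uses Day 14 data on either about 39 participants (Appendix 5's assumption) or all 60. With the pooled test, power is about 81% at 15 points and 75-79% with no SpO2 effect. The unpooled test is one to two points lower.

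**6. Second-look threshold.** All power figures above use CP < 4%. With the CP < 20% of 9.5 and no first look, power is 77.5-79.4% (79-81% with re-estimation).

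**The case against.** The strongest reply is that a flag is not a stop. Sections 9.2 and 9.5 require other endpoints to be weighed, and Appendix 5 calls the rule non-binding. This stands, and it limits the point. A reader might infer that the design as written cannot deliver its stated power. The documents do not support that: power is 81-84% if flags are not acted on and about 81% at a 15-point advantage under one natural reading of the rule. The figures of 33-74% belong to strict adherence, which the protocol does not prescribe.

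A reader might also infer that the criterion flags an effective drug one time in five. That holds only near an assumed 15-point advantage. For control rates of 20-70%, the rate runs from 29-32% at 10 points to 2-6% at 25 points.

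It can also be said that 9.2 speaks of the primary comparison, that its figure reproduces, that Appendix 5 discloses the omission, and that 9.5 leaves interim detail to the SAP and DMC Charter. All of that is true. A futility-only look also cannot inflate type I error. But the power claim, the size of the look, the numeric criterion and the NA entries are all fixed in this protocol. Section 9.2 states the 80% and the first futility look together without saying that the first excludes the second, and the appendix's remark about revisiting the look is an unfinished placeholder.

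**Conclusion.** The point holds in limited form. The approximately 80% in 9.2 excludes the first futility look that 9.2 and 9.5 make part of the design. The criterion applied there discriminates poorly: it is met in only 61-63% of cases with no SpO2 effect, yet in 17-20% with a true 15-point advantage.

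The cost in power ranges from nothing, if flags are overridden, to about 16 points at a 15-point advantage if every flag stops the trial (83% to 67%), and about 50 points if the drug prevents progression without changing room-air SpO2 (83% to 33%). Requiring an unfavourable progression trend as well removes most of that loss. These sizes rest on SpO2 responder rates that the protocol does not give, on complete Day 10 data, and on CP < 4% at the second look.

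**What to change.** 1. In 9.2 and Appendix 5, state that the approximately 80% holds only if the first-interim SpO2 criterion is not acted on.
2. In 10.5.2, replace the NA entries with the probability of meeting the criterion under stated SpO2 responder rates, and delete or complete the remark about revisiting the look.
3. Give overall power including the first look for the same SpO2 effects, both if every flag stops the trial and under the intended use of the other endpoints.
4. Reconcile the second-look CP threshold (20% in 9.5, 4% in Appendix 5) and use the retained value in these calculations.

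The cost is a few sentences, one short simulation and a less favourable stated power. Sample size, alpha and conduct do not change.

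Lowering the criterion to a difference below 0 is an option for the sponsor, not a correction. At a 15-point advantage and a control rate of 40-50%, it would cut the flag rate from about 20% to 11-12%. Power under strict adherence would still be only about 74%, and flags with no SpO2 effect would fall from 61% to 46%.

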9.3 Populations for Analyses

For purposes of analysis, the following analysis sets are defined:

Table 9-1 **Populations for Analysis**

Population (Analysis Set)	Description
Intent-To-Treat (ITT) Population	The ITT Population will include all randomized participants. The ITT participants will be analyzed according to randomized treatment, irrespective of the actual treatment received. Participants who withdraw from treatment early will be followed for the assessment of the Day 14 primary endpoint. All efficacy analyses will be performed using the ITT Population.
Per Protocol (PP) Population	The PP Population will include all participants in the ITT Population with no major protocol deviations that may significantly impact data integrity or patient safety. The PP Population will be used for supportive analyses of the efficacy measurements.
Safety Population (SP)	The SP will include all randomized participants who inhale any amount of study intervention or are randomized to the control arm. The SP will be analyzed according to the actual treatment received. This set will be used for the safety analyses.

The ITT Population will be the primary analysis set for all efficacy analyses and the PP Population will be used to demonstrate robustness of results for the primary efficacy endpoint.

9.4 Statistical Analyses

Below is a description of planned statistical analyses. Further details are presented in the Statistical Analysis Plan (SAP).

9.4.1 General Considerations

All statistical analyses will be conducted using SAS, Version 9.4 or later. Baseline characteristics will be summarized by treatment arm. For continuous measures the mean and standard deviation (SD) will be summarized. Categorical variables will be described by the proportion in each category. In addition, 95% confidence intervals (CIs) will be computed as indicated.

All the categorical variables including the primary endpoint will be summarized by treatment with the numbers and percentages of the participants. Treatment difference will be tested using a Cochran–Mantel–Haenszel test stratified by 1) country and 2) participant's clinical status at Baseline. For the categorical endpoints, relative risk and its 95% CI will be presented.

All of the continuous variables, including the changes from Baseline, will be summarized by treatment with the means, SD, medians and the ranges. The mixed model with repeated

measurements /analysis of covariance model with treatment, country, participant's clinical status at Baseline and visit as the model term, and Baseline value as the covariate will be used to test for the significance of the treatment difference. Least square means, standard errors, 95% CIs and p-values will be presented.

Time to event endpoints will be analyzed using the Cox Proportional Hazard model with treatment, participant's clinical status at Baseline and country as the model term. The hazard ratio of RESP301+SOC versus SOC will be presented along with 95% CI and p-value from the model. The Kaplan-Meier curves of the time to events will be presented by treatment for each applicable endpoint.

Handling of missing data

If participants are discharged from the hospital prior to Day 14 due to improvement of the clinical status and their status on Day 14 cannot be obtained, their status on Day 14 for the primary endpoint will be imputed with the status on the day of discharge. Depending on the reasons for missing data on the primary endpoint up to Day 14, additional sensitivity analyses will be performed. Further details on handling on missing data will be provided in the SAP.

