5.2 Inclusion Criteria

Participants are eligible to be included in the study only if all of the following criteria apply:

Age

1. Participant is ≥ 18 years of age, at the time of signing the informed consent.

Type of Participant and Disease Characteristics

2. Participant has laboratory-confirmed SARS-CoV-2 infection as determined by reverse transcriptase polymerase chain reaction (RT-PCR) or other approved clinical testing prior to randomization.
3. Participant is hospitalized in relation to COVID-19, requiring supplemental oxygen to maintain SpO₂ at a safe level (WHO level 4).

Sex

4. Participant is male or female. All females of childbearing potential, including pregnant females, must consent to urine pregnancy testing at screening to be eligible for the study. (Females who are not of childbearing potential do not need to undergo a pregnancy test at screening).

Informed Consent

5. Participant is capable of giving signed informed consent as described in Appendix 1 which includes compliance with the requirements and restrictions listed in the informed consent form (ICF) and in this protocol.

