6.3 Measures to Minimize Bias: Randomization and Blinding

This is an open-label study; however, the specific intervention to be taken by a participant will be assigned using an interactive voice response system (IVRS)/interactive web response system (IWRS). The site will contact the IVRS/IWRS prior to the start of study intervention

administration for each participant. The site will record the intervention assignment on the applicable case report form (CRF), if required.

Potential bias will be reduced using a central stratified randomization to assign participants into one of the study treatment arms, RESP301+SOC or SOC (control), with a randomization ratio of 2:1. Participants will be stratified by country and presence of risk factors for severe outcomes of COVID-19, based on comorbidities and age as follows:

1. Age >65 years
2. Ongoing or currently treated diabetes mellitus
3. Ongoing or currently treated hypertension
4. Ongoing or currently treated cardiovascular disease
5. Ongoing or currently treated chronic lung disease
6. Cancer history of less than 3 years, basal cell skin carcinoma excluded
7. Ongoing or currently treated chronic kidney disease

Participants will be stratified as no risk factor (none of the above criteria), one risk factor (one single of the above) or high-risk factor (2 or more of the above).

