10.5 Appendix 5: Statistical Design Considerations

10.5.1 Some General Design Considerations

1. Binary primary endpoint: progression to critical stage/death up to Day 14
 - to be analyzed by a Cochran-Mantel-Haenszel (CMH) stratified for the factors used in the stratified randomization
 - subjects who withdraw from study treatment will be followed up until their primary endpoint outcome is known (i.e., up to Day 14 or progression to critical stage/death, whatever is first)
 - it is, therefore, not clear what current protocol synopsis text could mean: *If subjects are discharged from the hospital prior to day 14 due to improvement of the clinical status and their status on day 14 cannot be obtained, their status on day 14 for the primary endpoint will be imputed with the status on the day of discharge. and what the implications on statistical study characteristics could be. Further discussion is needed.*
2. Timing of the two planned interim analyses with stopping options is stated as

There are 2 interim analyses planned, the first interim analysis after the first 60 participants have completed day 10 of the observation period ... and a second interim analysis after 150 participants have completed day 14 of the observation period.

With the current text for the timing of the first interim analysis, it is not clear how many subjects will have been randomized at least 14 days prior to the interim data cut-off date and can therefore provide data for the binary primary endpoint (“progression to critical stage/death up to Day 14”).

For such a binary endpoint, Parexel does not recommend including any participant randomized less than 14 days prior to the interim data cut-off date (note this would be different to a study with a time-to-event endpoint) as

- for such participants not yet progressed, the outcome up to Day 14 is unknown and should not be imputed as “not progressed up to Day 14”
- for such participants progressed prior to Day 14, the outcome is known but their inclusion would bias the estimation of progression probability up to Day 14 in a upwards direction.

In order to set up the adaptive group-sequential study design, the following assumptions have been used:

- first interim analysis: a total of ≈ 39 participants randomized at least 14 days prior to data cut-off date
- second interim analysis: a total of $\approx 50\%$ of the initially planned number of participants randomized at least 14 days prior to data cut-off date.

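### Section 9.4.1 and Appendix 5 give different strata for the primary CMH test, and Section 9.4.1 replaces the randomisation risk category with a factor that eligibility appears to hold constant

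*Protocol*

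**What the plan says.** Randomisation (Section 6.3): "Participants will be stratified by country and presence of risk factors for severe outcomes of COVID-19, based on comorbidities and age as follows". Seven risk factors are listed and collapsed to three levels: none, one, two or more.

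Analysis (Section 9.4.1): categorical endpoints, the primary explicitly among them, are compared by a CMH "test stratified by 1) country and 2) participant's clinical status at Baseline". Continuous endpoints use a repeated-measures model or an "analysis of covariance model with treatment, country, participant's clinical status at Baseline and visit as the model term", with the baseline value as covariate. The Cox model has treatment, baseline clinical status and country. The risk category is in none of the three.

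Appendix 5 (Section 10.5.1, item 1): the primary CMH is "stratified for the factors used in the stratified randomization". Section 4.2 also says, in general terms, that results will be stratified by the Section 6.3 risk factors.

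Eligibility (Section 5.2, criterion 3): "Participant is hospitalized in relation to COVID-19, requiring supplemental oxygen", identified there as WHO level 4.

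These passages are from Version 2.0. Version 1.0 has the same conflict, between its Section 9.4.1 and its Appendix 6. The statistical section of Version 3.0 is not in the text supplied, and the Amendment 2 change list names no change to Section 9.4.1 or Appendix 5.

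**The concern.** There are two problems.

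First, the primary test is specified in two incompatible ways. Sections 9.2 and 9.5 both send the reader to Appendix 5 for detail, so the appendix is operative text. An SAP that follows either passage departs from the other. In an open-label trial with an unblinded interim, the strata of the primary test should not be open to choice after data have been seen.

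Second, the factor named in Section 9.4.1 appears to do no work. In the objectives table, the objective on clinical status is measured by WHO-scale endpoints. The missing-data text of Section 9.4.1 uses the same term when it carries forward a status for the WHO-scale primary endpoint. The schedule of activities has clinical status rechecked against eligibility before the first dose. If the term means the WHO level, every eligible participant has the value 4. The analysis then ignores the risk category, which was made a stratification factor because it is expected to predict progression. A test that ignores a prognostic factor balanced by design uses too large a standard error, so it is conservative and gives up some power.

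**Working it through.** **1. The passages side by side**

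| Place | Factors for the primary CMH |
|---|---|
| Section 6.3 (randomisation) | country, risk category (3 levels) |
| Appendix 5, item 1 | the randomisation factors: country, risk category |
| Section 4.2 | results stratified by the Section 6.3 risk factors |
| Section 9.4.1 | country, baseline clinical status |

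A factor with one level creates no further strata. On the WHO-level reading, Section 9.4.1 is therefore exactly CMH by country.

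**2. The plan's own power figure**

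Section 9.2 states "approximately 80% power and alpha level 0.025 (one-sided) to demonstrate significant reductions (15% versus 30%) of the primary endpoint", with 200 and 100 participants.

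- Pooled rate: (100×0.30 + 200×0.15)/300 = 0.20
- SE under the null: √[0.20×0.80×(1/100 + 1/200)] = 0.0490
- SE under the alternative: √[0.30×0.70/100 + 0.15×0.85/200] = 0.0523
- Uncorrected: Φ[(0.15 − 1.960×0.0490)/0.0523] = 84.9%
- Continuity correction, subtracting ½(1/100 + 1/200) = 0.0075 from the difference: 81.3%
- Unpooled: Φ[0.15/0.0523 − 1.960] = 81.8%. Fisher exact: 81.4%.

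The stated figure is reproduced within 2 points by the corrected, unpooled and exact methods. The simulation below uses CMH without continuity correction, so its reference value is about 85%, not 80%.

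**3. Assumptions for the stratification effect**

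The protocol gives no event rate by risk category, no category sizes and no number of countries. Assumed: three equal risk categories, control rates averaging 30%, relative risk 0.5 in each, 2 or 5 equal countries with no country effect, and blocks of 3 within country-by-risk cells. The test is one-sided, because the Haybittle-Peto rule of Section 9.5 would "leave one-sided nominal alpha of 0.0249 for the final analysis". Only the final analysis at N = 300 is simulated, with 40,000 trials per scenario.

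**4. Results** (ranges cover 2 and 5 countries)

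| Control rates: none / one / two or more | Power, country only | Power, country × risk | Loss (points) | Type I error, country only |
|---|---|---|---|---|
| 30/30/30% | 85.3% | 85.2–85.3% | about 0 | 0.026 |
| 20/30/40% | 85.5–85.7% | 86.0–86.1% | 0.4–0.5 | 0.024–0.025 |
| 15/30/45% | 86.0% | 86.8–86.9% | 0.8–1.0 | 0.022–0.023 |
| 10/25/55% | 86.9% | 88.9–89.0% | 2.0–2.1 | 0.016 |

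The country × risk test has type I error 0.025–0.027 throughout. The Monte Carlo standard error is about 0.0008 for type I error, √(0.0249×0.9751/40,000), and about 0.2 points for power.

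**5. Analytic check of the type I error**

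With risk balanced between arms, the true null variance is proportional to the mean of p(1−p) within categories. The country-only test uses 0.30×0.70 = 0.21 instead. With R as the ratio of the two, the actual size is about 1 − Φ(1.9617/√R).

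- 20/30/40%: mean (0.16 + 0.21 + 0.24)/3 = 0.2033, R = 0.968, size 0.023
- 15/30/45%: mean (0.1275 + 0.21 + 0.2475)/3 = 0.195, R = 0.929, size 0.021
- 10/25/55%: mean (0.09 + 0.1875 + 0.2475)/3 = 0.175, R = 0.833, size 0.016

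These agree closely with the simulation.

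**The case against.** Several points on the other side have force.

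- **The risk category is not simply missing from the primary test.** A reader of Section 9.4.1 alone might infer that it is. Appendix 5 specifies the randomisation factors for the primary CMH, and Section 4.2 points the same way. For the primary endpoint the defect is a contradiction, not an omission. For the Cox and MMRM/ANCOVA models, only the general sentence in Section 4.2 points to the risk factors.
- **The WHO-level reading is an inference.** The term is never defined, and because that reading makes the factor empty, the phrase may be a mislabel for the risk category. This stands. It does not remove the need for correction, since an undefined stratum in the primary test also has to be resolved.
- **The test is not invalid.** A reader might infer false-positive inflation from a mis-specified stratum. The calculations show the opposite: size is near or below nominal.
- **The trial is not underpowered as a result.** At the planned effect, power under the country-only test is 85% or more in every scenario, above the stated figure. If risk is not prognostic, nothing is lost.
- **No loss was computed for the Cox or MMRM/ANCOVA models.** For SpO₂ and NEWS 2 the baseline value is already a covariate and may carry prognostic information, so the CMH figures should not be carried over.
- **The constant baseline covariate in the WHO-scale change model is harmless.** It is aliased with the intercept and leaves the treatment estimate unchanged.

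**Conclusion.** The point holds as a contradiction in the stated primary analysis, together with a factor in Section 9.4.1 that is either constant (on the protocol's own usage) or undefined. It should be corrected because a confirmatory test needs one stated set of strata. The power argument is secondary.

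The loss is about 0 to 2 points over assumed control rates from 30/30/30% to 10/25/55%. A still steeper assumption, 5/25/60%, gave 87.2% against 90.7%, or 3.5 points, in a separate simulation without a country factor. Type I error of the country-only test falls as risk becomes more prognostic, to about 0.016 at 10/25/55%. All these sizes rest on assumed rates and equal categories, since the protocol gives neither. The conclusion about the contradiction rests on the text alone. Whether the wording persists in the Version 3.0 statistical section cannot be confirmed from what is supplied.

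**What to change.** In Section 9.4.1, replace baseline clinical status with the three-level risk-factor category used at randomisation (none, one, two or more) in the CMH, MMRM/ANCOVA and Cox text. Keep country. Check that the result agrees with Section 4.2, Section 6.3 and Appendix 5, item 1, and that the SAP uses the same factors. If a different baseline measure was intended, define it and state it in addition to the risk category.

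Add a rule, fixed before any comparative data are seen, for pooling sparse country-by-risk cells. The number of countries is not stated, and three risk levels within each country can leave small cells.

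The cost is a short wording change and one added rule. No new data are needed, because the risk category must already be known to the IVRS/IWRS to randomise each participant. Removing the constant baseline value from the WHO-scale change model is optional tidying and changes no result.
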